16.1 Pharmacokinetics

PK evaluation will be performed at final analyses of Cohort A and Cohort B.

All statistical analyses and descriptive summaries of PK data will be performed on the PKAS.

Blood samples for all study cohorts and parts will be collected for enpatoran determination according to the following schedule:

Table 5: Pharmacokinetic Sampling Times

Day	Time (h)	Time from Scheduled Sampling Allowed
Day 1 and Day 15	Predose	Within 60 minutes prior to morning dose administration
	Between 1-2	
	Between 4-6	
Day 29 (Week 4) and Day 85 (Week 12)	Predose	Within 60 minutes prior to morning dose administration
Day 57 (Week 8)	Predose	Within 60 minutes prior to morning dose administration
	Between 1-2	
Day 113 (Week 16), Day 141 (Week 20) and Day 169 (Week 24)	Any time postdose	

16.1.1 Descriptive Statistics of PK Concentration Data

PK concentrations will be descriptively summarized by cohort, part, scheduled visit, and time window using: number of subjects included in the analysis set (N), number of non-missing observations (n), percent of non-missing observations (n %), arithmetic mean (Mean), standard deviation (SD), geometric mean (GeoMean), the geometric coefficient of variation (GeoCV), and the 95% confidence interval for the GeoMean (lower confidence interval [LCI] 95% GM, upper confidence interval [UCI] 95% GM),

minimum (Min), median (Median), and maximum (Max). PK samples that are collected at any time postdose (Week 16, Week 20, and Week 24) will be summarized by scheduled visit.

Descriptive statistics will only be calculated for n > 2 in which a measurement of below the lower limit of quantification represents a valid measurement and will be taken as zero for summary statistics of PK concentration data. In case $n \le 2$, individual data will be presented (min, max) in summary tables. If the calculated mean or GeoMean is BLQ then it shall be reported in outputs as BLQ; SD, GeoCV% shall be reported as not determined (ND); LCI, UCI, Min, Median, and Max shall be reported as BLQ if applicable.

Descriptive statistics of PK concentration data will be calculated using values with the same precision as the source data and rounded for reporting purposes only. PK concentrations will be carried over with full precision as provided in the source data without any rounding applied to CDISC SDTM PC and ADaM PC domains.

The following conventions will be applied when reporting descriptive statistics of PK concentration data:

N, n: 0 decimal place

Mean, GeoMean, Min, Median, Max, SD,

3 significant digits

LCI 95% GeoMean, UCI 95% GeoMean:

GeoCV: 1 decimal place

16.1.2 Descriptive Statistics of PK Parameter Data

PK parameter data will be descriptively summarized by cohort, part, and scheduled visit using: number of non-missing observations (n), arithmetic mean (Mean), standard deviation (SD), coefficient of variation (CV%), minimum (Min), median (Median), maximum (Max), geometric mean (GeoMean), the geometric coefficient of variation (GeoCV) and the 95% confidence interval for the GeoMean (lower confidence interval [LCI] 95% GM, upper confidence interval [UCI] 95% GM).

Descriptive statistics will only be calculated for a PK parameter when n > 2. In case $n \le 2$, individual data will be presented (min, max) in summary tables.

PK parameters read directly from the measurements (i.e., C_{trough}) will be reported with the same precision as the source data. All other PK parameters will be reported to 3 significant figures. Descriptive statistics of PK parameter data will be calculated using full precision and rounded for reporting purposes only.

PK parameters will be provided with full precision, without any rounding applied to CDISC SDTM PP and ADaM PP domains.

The following conventions will be applied when reporting descriptive statistics of PK parameter data:

n 0 decimal place

Mean, Min, Median, Max, GeoMean, 3 significant digits

95% CI, SD:

CV%, GeoCV%: 1 decimal place

16.1.3 General Specifications for PK Concentration and PK Parameter Data

The following checks for enpatoran concentrations will be performed. This is not a comprehensive list and additional checks may be required.

- Samples will be flagged and removed from the analysis if they do not have actual time of PK sampling and actual time of prior/last dose recorded.
- Predose or trough samples which have been taken after the subsequent dosing will be reported as a protocol deviation. The resulting concentrations will be included in concentration listings but excluded from descriptive statistics of concentrations and from PK parameter estimation.
- If predose samples are collected outside of the hour prior to the morning dose administration, these will be excluded from the concentration summary and mean/median concentration plots.
- If the subject misses the last dose before the PK blood collection, the sample should be collected and presented in listings but flagged and excluded from the NCA analysis but not from Population PK analysis.
- Postdose samples that are collected outside specified time windows will be excluded from concentration summaries and mean/median concentration plots only for Weeks 1, 2 and 8.
- If an episode of vomiting occurs on the day of PK collection, the concentration results for that day will be flagged and identified in a listing. If it is known that the time of vomiting is after the time of enpatoran dosing, and prior to collection of a PK sample on the day of the PK collection, the concentration results following the time of vomiting will be excluded from the calculation of summary statistics.
- If a PK sample is collected outside of the blood collection window on days when there is a collection window specified in Table 1 Schedule of Assessments in the protocol (excluding Weeks 16, 20 and 24), the affected concentration results will be flagged and identified in a listing but will be excluded from NCA calculation and its summary statistics.

Values below the lower limit of quantification (BLQ) will be taken as zero for summary statistics of PK concentration data, PK parameter estimation (e.g., C_{trough}), and for graphical presentations.

INFORMATION

Missing concentrations (e.g., no sample, insufficient sample volume for analysis, no result or result not valid) will be reported and used generally as "N.R.". A participant who withdraws prior to the last planned observation will be included in the analyses up to the time of discontinuation.

PK concentrations which are erroneous due to a sampling processing or analytical error (as documented in the bioanalytical report) may be excluded from the PK analysis if agreed by the Sponsor. In this case the rationale for exclusion will be provided in the CSR. Any other PK concentrations that appear implausible to the Clinical Pharmacologist/Clinical PK/PD Scientist will not be excluded from the analysis. Any implausible data will be documented in the CSR.

If other important protocol deviations occurred likely to affect the PK profile of participants, the impacted concentrations and PK parameters will be excluded from summary statistics and further statistical evaluation.

Any PK concentrations or PK parameters excluded from summary statistics will be included in participants listings and flagged; a reason for exclusion will be detailed in the CSR (e.g., a footnote or a table of exclusions). Any flags should be included in the study specific CDISC data sets.

PK concentrations and PK parameters excluded from summary statistics will not be included in mean/median figures. Mean/median plots will only contain values where n > 2. In case ≤ 2 , individual participant profiles may be included in mean/median plots.

16.1.4 Estimation of Pharmacokinetic Parameters

The computer program Phoenix® WinNonlin® version 8.3, or higher (Certara, L.P., Princeton, New Jersey, USA) will be used to derive PK parameters applying non-compartmental analysis (NCA).

The statistical software SAS® (Statistical Analysis System, SAS-Institute, Cary NC, USA, windows version 9.1 or higher) may be used to generate additional PK parameters, produce tables, listings and figures.

16.1.4.1 Estimation of Pharmacokinetic Parameters in Plasma

In cases where actual dosing time is missing, scheduled time might be used for NCA after performance of adequate plausibility checks and agreement with the sponsor. Decision and rationale should be included in the CSR. There will be no imputation of missing data.

The following plasma PK parameter will be calculated where appropriate:

Symbol	Definition
C_{trough}	The concentration observed at the end of dosing interval immediately before next dosing

C_{trough}/Dose The dose normalized concentration observed at the end of dosing interval immediately before next dosing

Additional PK parameters may be calculated where appropriate.

Units for PK parameter output will be based on concentration units used in the study, unless otherwise specified. In case concentration data units change within the study, PK parameters will be reported using consistent units throughout study outputs.

The parameter C_{trough}, will be obtained directly from the concentration-time profiles

16.1.5 Presentation of PK Concentration and PK Parameter Data

16.1.5.1 Listings and Tables

The following PK tables will be produced (PK Analysis Set):

- Individual and descriptive statistics of concentrations by cohort, part, scheduled visit, and time window
- Individual and descriptive statistics of PK parameters by cohort, part, and scheduled visit
- Individual and descriptive statistics of dose normalized PK parameters by cohort, part, and scheduled visit

[figure not shown]
The following PK Listings will be produced (Safety Analysis Set):

- PK Sampling date, actual time, nominal time, deviation from time, percentage time deviation and concentration by participant analyte, matrix and group sorted in chronological order
- Concentration/PK parameter excluded from summaries/analyses

18.1 Clinical Questionnaires

[figure not shown]

[figure not shown]

18.2 Corticosteroid Usage

18.2.1 General rules

To perform derivations with regards to CS use at Baseline or during the on-treatment period, the following rules will be applied:

- CS will be medications collected in the "CORTICOSTEROID MEDICATION DETAILS" eCRF form. CS collected in the "CONCOMITANT MEDICATIONS DETAILS" eCRF form will also be considered. Only CS for which indication is related to lupus (reason for medication = Disease related condition) will be considered.
- To derive topical CS use at Baseline, only CS medications with route = topical will be considered.
- To derive systemic CS use, only CS medications with route = oral, intravenous (including 'IV drip' and 'IV bolus'), intra-articular and intramuscular will be considered. Prednisone-equivalent CS dose will be derived for systemic use only.
- Concomitant CS medications are CS medications which are taken by participants any time during the on-treatment period, see section 9.8.
- When dose per administration or dosing frequency is missing or uninterpretable, the corresponding CS will not be included in CS dose derivation.

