8.2 Subgroup Definition and Parameterization

Subgroup analyses will be performed for primary efficacy variables (BICLA response at Week 24 in Cohort B [section 14.2.5], CLASI-A total score at Week 16 in Cohort A [section 14.1.6]), selected key secondary variables (SRI-4 response at Week 24 in Cohort B [14.3.6]), and CCI

The category "missing" will not be included in any subgroup analysis. In Cohort A, subgroup analysis will be performed if at least 5 participants are observed in all subgroup levels for each study intervention group. The threshold will be set to 10 for subgroup analyses in Cohort B.

• Systemic CS use at Baseline: low/medium (daily prednisone-equivalent dose < 10 mg), high (daily prednisone-equivalent dose ≥ 10 mg)

The following subgroups will be defined for Cohort A only:

• Disease diagnosis (CLE only, SLE)

CLE only: "Does the subject have a diagnosis of SLE" = No and participant has DLE and/or SCLE

SLE: "Does the subject have a diagnosis of SLE" = Yes

• CLASI-A total score at Baseline: $< 10, \ge 10$

The following subgroups will be defined for Cohort B only:

• Ethnicity: Japanese, non-Japanese

The following subgroups will be defined for Cohort B with CLASI $A \ge 8$ at Screening and confirmed at Day 1:

• CLASI-A total score at Baseline: $< 10, \ge 10$

9 General Specifications for Data Analyses

Unless otherwise specified, data will be summarized for each cohort (Cohort A, Cohort B) separately.

Study intervention groups will be labeled placebo, enpatoran 25 mg BID and enpatoran 50 mg BID, enpatoran 100 mg BID, as applicable for the cohort/part. Study intervention groups may also be referred as "dose levels".

Unless otherwise specified, comparisons will be presented for each active dose of study intervention versus placebo. Results from different study intervention groups will be presented in increasing order of dose level (placebo on the left).

Unless otherwise specified, continuous variables will be summarized using descriptive statistics, i.e., the number of participants with non-missing values (n), mean, standard deviation, median, 25th percentile (Q1) and 75th percentile (Q3), minimum, and maximum.

Qualitative variables will be summarized by frequency counts and percentages. Unless otherwise stated the calculation of proportions will be based on the number of participants of the analysis set of interest. Therefore, counts of missing observations will be included in the denominator and presented as a separate category.

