Attributes of the estimands are described in the table below:

Endpoint	Clinically meaningful CS reduction, defined as reduction of daily prednisone-equivalent dose from ≥ 10 mg at Day 1 to ≤ 5 mg by the Week 12 visit and sustained through Week 24
Population(s)	 SLE participants (Cohort B) with daily prednisone-equivalent dose ≥ 10 mg at Day 1 Cohort A participants with daily prednisone-equivalent dose ≥ 10 mg at Day 1
Treatment	Enpatoran vs placebo
Population-level summary measure	Odds ratio (conditional on stratification factors) between each active dose and placebo

Clinically meaningful CS reduction at Week 12 will be assessed based on the "CORTICOSTEROID MEDICATION DETAILS" form. Sustainment of the reduction will be assessed throughout the period between Week 12 and Week 24 (see appendix 18.2 for derivation of daily prednisone-equivalent dose).

A composite estimand strategy will be applied to handle the intercurrent events. Participants who experience any of these intercurrent events will be considered as not achieving CS reduction.

Descriptive Analysis

The number and percentage of participants with a clinically meaningful CS reduction will be provided.

Inferential Analysis

A logistic regression of clinically meaningful CS reduction status (yes/no) on the study intervention groups as a categorical variable and the stratification factors (see Section 14) will be fitted.

Odds ratios together with their 95% CI will be provided for each enpatoran group vs placebo. Treatment effect (and 95% CI) on the probability scale will also be provided.

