14.3.4 BICLA Response and Clinically Meaningful CS Reduction

This estimand will be analyzed at the final analysis. Its attributes are described in the table below:

Endpoint	BICLA response and clinically meaningful CS reduction, defined as reduction of daily prednisone-equivalent dose from ≥ 10 mg at Day 1 to ≤ 5 mg by the Week 12 visit and sustained through Week 24
Population(s)	SLE participants (Cohort B) with daily prednisone-equivalent dose ≥ 10 mg at Day 1
Treatment	Enpatoran vs placebo

Population-level	Odds ratio (conditional on stratification factors) between each active dose and placebo
summary measure	

A composite estimand strategy will be applied to handle the intercurrent events. Participants who experience any of these intercurrent events will be considered as non-responder.

Participants will be considered as responders if they have a BICLA response at Week 24 and a clinically meaningful CS reduction from ≥ 10 mg at Day 1 to ≤ 5 mg by the Week 12 visit sustained through Week 24 was observed (see section 14.3.3). If BICLA response is missing at Week 24, it will be considered as a non-response (see Section 14.2.1).

Descriptive Analysis

The number and percentage of participants with a BICLA response and a clinically meaningful CS reduction will be provided.

Inferential Analysis

A logistic regression of the BICLA response and clinically meaningful CS reduction status (yes/no) on the study intervention groups as a categorical variable and the stratification factors will be fitted.

Odds ratios together with their 95% CI will be provided for each enpatoran group vs placebo. Treatment effect (and 95% CI) on the probability scale will also be provided.

14.3.5 CLA-IGA 0 or 1 at Week 16 and Week 24

Estimands attributes are described in the table below.

Endpoint(s)	 Occurrence of CLA-IGA 0 or 1 at Week 16 Occurrence of CLA-IGA 0 or 1 at Week 24
Population(s)	 Cohort A Cohort B with CLASI-A ≥ 8 at Screening and confirmed at Day 1
Treatment	Enpatoran vs placebo
Population-level summary measure	Odds ratio (conditional on stratification factors) between each active dose and placebo

Descriptive Analysis

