The number and percentage of participants who have a CLA-IGA score of 0 or 1 ("clear" or "almost clear") will be provided at each scheduled visit. Participants experiencing an intercurrent event prior to the visit of interest will be considered as not having a CLA-IGA score of 0 or 1. A line plot depicting the percentage of responders over time grouped by study intervention group will also be provided.

Inferential Analysis

The same analysis as described in section 14.3.3 will be performed to assess the treatment effect on the occurrence of CLA-IGA 0 or 1 at Week 16 and Week 24.

Some CLA-IGA assessments have been conducted while Investigators were not trained. To assess the impact of the training on the results observed, descriptive and inferential analyses described in this section will be replicated using assessments collected on or after Investigator's training only.

14.3.6 SRI-4 Response through Week 24

This analysis will be conducted at the final analysis. Attributes of the estimand are described in the table below.

Endpoint	Systemic lupus erythematosus Responder Index-4 (SRI-4) response at Week 24
Population(s)	SLE participants (Cohort B)
Treatment	Enpatoran vs placebo
CCI	
Population-level summary measure	Odds ratio (conditional on stratification factors) between each active dose and placebo

The systemic lupus erythematosus responder index-4 (SRI-4) response is a measure of reduced SLE disease activity. A participant is an SRI-4 responder at a given time-point if they achieve:

- CC
- No worsening of ≥ 0.3 points in PGA of SLE disease activity score compared to Baseline (PGA score expressed on a 0-3 scale) AND
- No new BILAG A organ domain scores and ≤ 1 new BILAG B organ domain score compared to Baseline using BILAG 2004

Imputation of missing items will be performed for CCI, PGA of SLE disease activity and BILAG questionnaires as described in section 9.11. If SRI-4 response is still missing after imputation at a visit, the participant will be considered as a non-responder.

Descriptive Analysis

SRI-4 response will be summarized using descriptive statistics (frequency and percentage) at each ontreatment scheduled visit. The number and percentage of participants meeting each SRI-4 component

[figure not shown]
criterion will be provided during the on-treatment period. Additionally, a line plot depicting the percentage of responders over time grouped by study intervention group will also be provided.

Inferential analysis

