A logistic regression of SRI-4 response at Week 24 on the study intervention groups as a categorical variable and the stratification factors will be conducted.

Odds ratio together with its 95% CI will be provided at Week 24 for each enpatoran group vs placebo. Treatment effect (and 95% CI) on the probability scale will also be provided. In addition, observed SRI-4 response (yes/no) will be summarized at each scheduled timepoint.

Subgroup analysis

14.3.7 LLDAS Attainment through Week 24

This analysis will be conducted at the final analysis. Attributes of the estimand are described in the table below.

Endpoint	LLDAS attainment at Week 24
Population(s)	SLE participants (Cohort B)
Treatment	Enpatoran vs placebo
Population-level summary measure	Odds ratio (conditional on stratification factors) between each active dose and placebo

Lupus low disease activity state (LLDAS) is attained at a specific visit if the following criteria are met at the visit (Golder 2020):

CCI

- o Renal, central nervous system, cardio-pulmonary: all descriptors of the system should be absent at the visit
- O Vasculitis: vasculitis descriptor of musculoskeletal system should be absent
- o Fever: fever descriptor of constitutional system should be absent
- No new descriptors of lupus disease activity compared with the assessment of the previous analysis visit

- PGA (scale 0-3) ≤ 1
- Daily prednisolone-equivalent dose \leq 7.5 mg from the day after the previous visit until the day of the current visit (see appendix 18.2 for derivation of daily prednisone-equivalent dose). If the previous visit is missed, the daily prednisolone-equivalent dose should be below or equal to 7.5 mg from 27 days prior to the current visit until that visit.
- Standard maintenance dosages of immunosuppressive drugs and approved biological agents

 This criterion will not be specifically programmed but is covered via the handling of the intercurrent event "protocol-prohibited medications as determined by EAC".

A composite estimand strategy will be applied to handle the intercurrent events: participants who experience any of these intercurrent events will be considered as not attaining LLDAS at all subsequent analysis visits.

Descriptive Analysis

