LLDAS attainment will be summarized using descriptive statistics (frequency and percentage) at each on-treatment scheduled visit. Additionally, a line plot depicting the percentage of responders over time grouped by study intervention group will also be provided.

Inferential analysis

A logistic regression of LLDAS attainment (yes/no) at Week 24 on the study intervention groups as a categorical variable and the stratification factors will be fitted.

Odds ratios together with their 95% CI will be provided for each enpatoran group vs placebo. Treatment effect (and 95% CI) on the probability scale will also be provided.

INFORMATION

14.3.8 Remission Attainment through Week 24

This analysis will be conducted at the final analysis. Attributes of the estimand are described in the table below.

Endpoint	Remission attainment at Week 24
Population(s)	SLE participants (Cohort B)
Treatment	Enpatoran vs placebo
Population-level summary measure	Odds ratio (conditional on stratification factors) between each active dose and placebo

Remission attainment per 2021 DORIS definition (Vollenhoven 2021) is defined at a specific visit as meeting the following criteria at the visit:

- · CCI
- PGA of SLE < 0.5 (0-3 scale)
- Daily prednisolone-equivalent dose ≤ 5 mg from the day after the previous visit until the day of the current visit (see appendix 18.2 for derivation of daily prednisone-equivalent dose). If the previous visit is missed, the daily prednisolone-equivalent dose should be below or equal to 5 mg from 27 days prior to the current visit until that visit.
- Stable immunosuppressives including biologics

This criterion will not be specifically programmed but is covered via the handling of the intercurrent event "protocol-prohibited medications as determined by EAC".

Imputation for CCl is described in section 9.11.2 and section 9.11.4 respectively. If at least one criterion for remission is not evaluable at a visit, remission will be considered as non-attained at the visit.

Descriptive Analysis

Remission attainment will be summarized using descriptive statistics (frequency and percentage) at each on-treatment scheduled visit. Additionally, a line plot depicting the percentage of responders over time grouped by study intervention group will also be provided.

Inferential analysis

A logistic regression of remission attainment (yes/no) on the study intervention groups as a categorical variable and the stratification factors will be fitted.

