18.2.4 Corticosteroid usage, daily dose

Prednisone-equivalent daily dose (mg) by visit (post-baseline visits):

• Prednisone-equivalent CS daily dose is equal to the total dose (mg) the participant is receiving at the date of the scheduled visit + 1 day (using conversion rules specified in section 18.2.3). If several CS are taken at the same scheduled visit, then all CS doses should be added.

CS dosing at Baseline is defined at CS dose taken the day of baseline visit (Day 1).

Signature Page for VV-CLIN-324916 v4.0

Approval Task	PPD
	13-Dec-2024 10:00:07 GMT+0000

Signature Page for VV-CLIN-324916 v4.0

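### Steroid records with an unknown dose or frequency add 0 mg to the derived daily dose, so four secondary endpoints can count an unknown dose as meeting the threshold

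*SAP*

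**What the plan says.** SAP 18.2.1 limits the prednisone-equivalent dose to systemic, lupus-related corticosteroid (CS) records and ends with this rule: "When dose per administration or dosing frequency is missing or uninterpretable, the corresponding CS will not be included in CS dose derivation". SAP 18.2.4 builds the daily dose by summation: "If several CS are taken at the same scheduled visit, then all CS doses should be added". SAP 18.2.2 treats incomplete dates differently: they are imputed and the record is kept.

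The derived dose is used in these places:

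- **CS reduction (SAP 14.3.3, Cohorts A and B):** at least 10 mg at Day 1, falling to 5 mg or less by Week 12. "Sustainment of the reduction will be assessed throughout the period between Week 12 and Week 24".
- **BICLA plus CS reduction (SAP 14.3.4, Cohort B):** the same dose criterion.
- **LLDAS (SAP 14.3.7, Cohort B):** a dose no higher than "7.5 mg from the day after the previous visit until the day of the current visit".
- **Remission (SAP 14.3.8, Cohort B):** 5 mg or less over the same kind of interval.
- **Baseline CS subgroup (SAP 8.2):** below 10 mg versus 10 mg or more.

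Only the remission section, in the readable text, says what happens when a component cannot be assessed: "If at least one criterion for remission is not evaluable at a visit, remission will be considered as non-attained at the visit".

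**The concern.** In a sum, leaving a record out is the same as entering 0 mg for it. The record itself shows that a systemic steroid was taken; only the amount is unknown. Doses cannot be negative, so the error runs one way. After baseline it can only move a participant towards meeting the 5 mg or 7.5 mg limit.

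The remission rule on non-evaluable criteria does not help, because a partial sum is a number and looks evaluable. If the excluded record is the participant's only one, the SAP does not say whether the empty sum is 0 mg or missing. Read literally it is 0 mg, the same as for someone on no steroid.

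At stake are the responder rates for the four secondary endpoints and the label of some participants in the baseline CS subgroup.

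**Working it through.** The plan gives no figure on this point, so there is none to reproduce. The check applies the rule to examples and then sizes the effect under stated assumptions.

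**Step 1: what the rule returns.** Derived dose = sum over usable records of dose × prednisone factor × frequency factor. From SAP Table 6: prednisone 1, methylprednisolone 1.25 (this agrees with Protocol Table 10: 1/0.8 = 1.25). From SAP Table 7: QOD 0.5, QD 1, BID 2, QAM 1, QPM 1. The doses below are illustrations.

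| Records | Derived | If the gap were filled |
|---|---|---|
| Prednisone 5 mg QD + methylprednisolone 4 mg, frequency missing | 5 mg | 5 + 4 × 1.25 × f = 7.5 (QOD), 10 (QD), 15 mg (BID) |
| Prednisone 5 mg QAM + prednisone 5 mg, frequency missing | 5 mg | 5 + 5 × 1 = 10 mg (QPM) |
| Prednisone 7.5 mg alone, frequency missing | empty sum | 3.75 (QOD), 7.5 (QD), 15 mg (BID) |
| Day 1: prednisone 7.5 mg QD + methylprednisolone 4 mg, frequency missing | 7.5 mg | 7.5 + 4 × 1.25 × 1 = 12.5 mg (QD) |

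In the first row the derived dose meets every limit. All three filled-in values fail 5 mg; QD and BID also fail 7.5 mg. In the third row the literal result (0 mg) meets every limit, while QOD would truly meet 5 mg and QD would truly meet 7.5 mg. The rule is therefore not always wrong; it is wrong only in one direction.

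**Step 2: how many people.** Protocol 9.2 gives the base-plan Cohort B arms: Part 1 is 60 at 2:1 (40 and 20) and Part 2 is 280 over four arms (70 each). Cohort A has 25 per arm. Assumptions, none of them in the documents: a share s = 25 to 50% are on 10 mg or more at Day 1; true CS-reduction rates p are 30% on placebo and 50% on 100 mg, with the other active arms between; and m = 2 to 10% of true non-responders have an excluded record that decides the outcome. Here m is not the rate of incomplete records, which would be higher.

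People misclassified = (1 − p) × n × s × m. One person moves the CS-reduction rate by 100/(n × s) points.

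| Arm | n | p | Misclassified | One person |
|---|---|---|---|---|
| Placebo | 20 + 70 = 90 | 30% | 0.315 to 3.15 | 2.2 to 4.4 points |
| 100 mg | 40 + 70 = 110 | 50% | 0.275 to 2.75 | 1.8 to 3.6 points |
| 25 or 50 mg | 70 | 30 to 50% | 0.175 to 2.45 | 2.9 to 5.7 points |
| Cohort A arm | 25 | 30 to 50% | 0.06 to 0.88 | 8.0 to 16.0 points |

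LLDAS and remission use the whole Cohort B arm, so one person moves them by 100/n = 1.1 (placebo), 0.9 (100 mg) or 1.4 points (25 or 50 mg).

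**Step 3: effect on the comparison.** With equal misclassification the observed rate is p' = p + (1 − p)m.

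| m | Placebo | 100 mg | Difference | Odds ratio |
|---|---|---|---|---|
| 0 | 30.0% | 50.0% | 20.0 | 2.33 |
| 2% | 31.4% | 51.0% | 19.6 | 2.27 |
| 5% | 33.5% | 52.5% | 19.0 | 2.19 |
| 10% | 37.0% | 55.0% | 18.0 | 2.08 |

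Both rates rise and the contrast shrinks slightly.

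**The case against.** **Existing rules cover part of this.** Protocol Appendix 7, Table 8 forbids starting or increasing steroids between Weeks 12 and 24. Protocol Appendix 8 counts steroid use outside the protocol rules, as judged by the EAC, as BICLA treatment failure. SAP 14.3.7 and 14.3.8 refer to an EAC-determined prohibited-medication event, and 14.3.3 and 14.3.4 apply a composite strategy to intercurrent events. The event lists are partly redacted. A reader might infer that any steroid added late with no frequency recorded escapes as a success; the documents do not support that. What remains is the incomplete record of an ongoing steroid. Protocol 6.8.1 requires tapering only as tolerated, so staying above 5 mg is not in itself a breach.

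**The SAP uses available data elsewhere.** A reader might infer that the rule contradicts a uniform policy, since "If BICLA response is missing at Week 24, it will be considered as a non-response" (14.3.4) and "If SRI-4 response is still missing after imputation at a visit, the participant will be considered as a non-responder" (14.3.6). Those rules concern a whole missing response. FACIT-Fatigue is prorated (9.12.2), Skindex averages the answered items (9.12.1), and AE severity takes the worst non-missing grade (15.1). So there is no uniform policy to contradict. Still, prorating and averaging do not set the missing item to 0, as the steroid rule in effect does.

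**The fix also misclassifies.** If it turned 5% of true responders into non-responders (equally an assumption), the rates would be 0.95 × 30 = 28.5% and 0.95 × 50 = 47.5%: a difference of 19.0 points, the same as the current rule at 5%, and an odds ratio of (0.475/0.525)/(0.285/0.715) = 2.27. This stands. The case for the fix is that it does not credit success on an unknown dose and makes the extent visible, not that it removes error.

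**Frequency.** Queries, a dedicated steroid form, review of steroid use by the Medical Monitor and EAC, and the free-text mappings in Table 7 make decisive incomplete records uncommon. This also stands.

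**Conclusion.** The concern holds in a limited form. Followed exactly, SAP 18.2.1 and 18.2.4 give a dose that can only be too low, and the readable text has no step that marks it as not evaluable. Four Cohort B secondary endpoints, CS reduction in Cohort A and the baseline CS subgroup are exposed. Under the assumptions above, 0.2 to 3.2 people per Cohort B arm would be misclassified, and the odds ratio would fall from 2.33 to no lower than 2.08.

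A reader might infer that the rule favours enpatoran. Nothing in the documents shows incomplete records to be more common in one arm; under blinding, the expected effect is higher rates in all arms with slight dilution. Nor are the primary endpoints directly affected: the readable criteria for CLASI-A and BICLA in the SAP do not use the derived dose, and Protocol 9.4 makes secondary p-values nominal. The change is worth making because it is cheap, not because the present rule threatens the main conclusions. The conclusion is limited to the unredacted text.

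**What to change.** Replace the last rule of SAP 18.2.1 with wording to this effect: if a systemic, lupus-related steroid record is active in the assessment window and its dose or frequency is still unusable after query, the dose criterion is not evaluable and counts as not met for CS reduction, BICLA plus CS reduction, LLDAS and remission, unless the usable records alone already decide it.

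Also:

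- State that no steroid record means 0 mg, and that a sum emptied by exclusions is missing.
- At Day 1, where usable records do not reach 10 mg and an incomplete record exists, label the baseline CS subgroup as missing, not below 10 mg. SAP 8.2 already says that this category "will not be included in any subgroup analysis". This corrects the label only; it does not change or restore the population on 10 mg or more.
- Report affected records and participants by arm.
- Keep the current rule as a sensitivity analysis. Records that fall in the window only through date imputation (18.2.2) can stay under the current rule, since it is not known that the steroid was being taken. They then add 0 mg in both analyses, so the pair should not be described as bracketing the rate for those participants.

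The cost is SAP wording, one programming flag and one count table. Some true responders with incomplete records will count as non-responders, and because sustainment runs from Week 12 to Week 24, one unresolved record in that period can be enough. The sensitivity analysis will show how many.
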